# 13.1.3.2 Analysis of the Primary Endpoint

The following analyses will be performed for the primary endpoint, defined as the change from baseline in 6MWD at Week 24:

- (1) Primary analysis
  - To evaluate the efficacy of TAS-205 appropriately, summary statistics will be calculated for each treatment group in the PPS.
- (2) Sensitivity analysis for the primary analysis
  - The analysis described in (1) will be performed in the FAS.

(3) Secondary analyses of the primary endpoint

The following analyses will be performed in the PPS and FAS:

- A 2-sample t-test will be performed between each treatment group and placebo group. This analysis will be performed with and without the LOCF imputation.
- The treatment effect will be estimated using the MMRM. The changes from baseline in 6MWD measured at other time points will also be included in this analysis.
- Using the MMRM, the dose relationship will be analyzed with treatment contrasts of (placebo group, low-dose group, high-dose group) = (-2 1 1), (-1 0 1), and (-1 -1 2). The changes from baseline in 6MWD measured at other time points will also be included in this analysis.

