#### 5. Primary Analysis

The following analyses will be performed for the primary endpoint, defined as the change from baseline in 6-minute walk distance (6MWD) at Week 24:

- (1) To evaluate the efficacy of TAS-205 appropriately, summary statistics will be calculated for each treatment group in the PPS.
- (2) As sensitivity analysis, the analysis described in (1) will be performed in the FAS.

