#### **6.1** Analysis of the Primary Endpoint

The following analyses will be performed in the PPS and FAS:

The following analyses will be performed for the primary endpoint, defined as the change from baseline in 6MWD at Week 24: Analysis will also be conducted in the group combining the low-dose group and the high-dose group excluding the analysis of MMRM.

- A 2-sample t-test will be performed between each treatment group and placebo group. This analysis will be performed with and without the LOCF imputation. Analyses will also be conducted with the following baseline definitions.
  - (1) Analysis excluding the subjects for whom the value of (6MWD on Day 1 6MWD at screening)/6MWD at screening is 0.2 or higher or -0.2 or lower
  - (2) Analysis using the mean value of 6MWD on Day 1 and 6MWD at screening as the baseline value
- With respect to the above analysis, subgroup analysis will be conducted for the following items.

Subgroup analysis: Presence or absence of the history of steroid use, age category ( $\geq$ 5 years and <7 years, and  $\geq$ 7 years), and baseline 6MWD (<350 m, and  $\geq$ 350 m)

- The treatment effect will be estimated using the MMRM. The changes from baseline in 6MWD measured at other time points will also be included in this analysis. Covariates will be the assigned group, baseline value, time point, and the interaction term of the assigned group and time point.
- Using the MMRM, the dose relationship will be analyzed with treatment contrasts of (placebo group, low-dose group, high-dose group) = (-2 1 1), (-1 0 1), and (-1 -1 2). The changes from baseline in 6MWD measured at other time points will also be included in this analysis. Covariates will be the assigned group, baseline value, time point, and the interaction term of the assigned group and time point.
- For the above 2 analyses, analyses will be conducted in the PPS by adding age and the presence or absence of the history of steroid use to explanatory variables. In addition, subgroup analysis will be conducted for the following items.

Subgroup analysis: Baseline 6MWD ( $\leq$ 350 m, and  $\geq$ 350 m)

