#### O MMRM

The confidence coefficient for estimation of confidence interval will be 2-sided 95%. In the analysis of MMRM, SAS MIXED procedure will be used as shown in the following SAS code.

proc mixed data = INDATA;

class	ATRTN † (ref='1'[Placebo]) AVISITN † SUBJID † ;
model	$AVAL^{\dagger} = BASE^{\dagger} ATRTN AVISITN ATRTN*AVISITN / ddfm = KR ;$
lsmeans	ATRTN*AVISITN / diff cl alpha = 0.05 ;
repeated	AVISITN / subject = SUBJID type = $UN^{\#}$ ;
estimate	"Low Dose TAS-205 Saturation - Week 12" ATRTN -2 1 1 ‡
	ATRTN*AVISITN $-2\ 0\ 1\ 0\ 1\ 0$ / cl alpha = 0.05;
estimate	"Low Dose TAS-205 Saturation - Week 24" ATRTN -2 1 1 ‡
	ATRTN*AVISITN $0 - 2 0 1 0 1 / cl alpha = 0.05$ ;
estimate	"Placebo vs High Dose TAS-205 - Week 12" ATRTN -1 0 1 ‡
	ATRTN*AVISITN $-100010$ / cl alpha = 0.05;
estimate	"Placebo vs High Dose TAS-205 - Week 24" ATRTN -1 0 1 ‡
	ATRTN*AVISITN $0 - 1 0 0 0 1 / cl alpha = 0.05$ ;
estimate	"High Dose TAS-205 Saturation - Week 12 " ATRTN -1 -1 2 ‡
	ATRTN*AVISITN $-1 \ 0 \ -1 \ 0 \ 2 \ 0 \ / \ cl \ alpha = 0.05$ ;
estimate	"High Dose TAS-205 Saturation - Week 24 " ATRTN -1 -1 2 ‡
	ATRTN*AVISITN $0 - 1 0 - 1 0 2 / cl alpha = 0.05$ ;

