#### run;

- ATRTN: Treatment group (placebo group [reference group], low-dose group, high-dose group)
   AVISITN: Time point (Week 12, Week24)
  - SUBJID: Patient ID

AVAL: Response variable

BASE: Baseline value

- Contrast coefficient (-2 1 1): Paired comparison of low-dose group saturation Contrast coefficient (-1 0 1): Paired comparison of linear trend Contrast coefficient (-1 -1 2): Paired comparison of high-dose group saturation
- # If convergence is not achieved with UN, TOEP will be used. If convergence is not achieved yet, the following will be used in this order:  $AR(1) \rightarrow CS \rightarrow VC$ .

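### The secondary MMRM of 6MWD applies one baseline slope to Week 12 and Week 24; a baseline-by-visit term would remove a conditional error at almost no cost

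*SAP*

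**What the plan says.** The primary analysis of change in 6MWD at Week 24 is descriptive. SAP 5 says: "To evaluate the efficacy of TAS-205 appropriately, summary statistics will be calculated for each treatment group in the PPS"; this is repeated in the FAS. Protocol 13.1.3.2 places the MMRM under "Secondary analyses of the primary endpoint", together with t-tests, for which SAP 6.1 says: "A 2-sample t-test will be performed between each treatment group and placebo group".

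For the MMRM, SAP 6.1 gives the fixed effects: "Covariates will be the assigned group, baseline value, time point, and the interaction term of the assigned group and time point". The code in SAP 8.3 agrees. After BASE, the MODEL statement continues "ATRTN AVISITN ATRTN*AVISITN / ddfm = KR", with no product of BASE and AVISITN. The code's legend lists two time points, Week 12 and Week 24. The covariance is unstructured at first, and: "If convergence is not achieved with UN, TOEP will be used". AR(1), CS and VC follow if needed.

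SAP 6.2.1(2) and 6.3 use the same covariate list for the other efficacy endpoints and for the pharmacodynamic and exploratory endpoints.

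**The concern.** A single baseline coefficient assumes that starting 6MWD predicts change equally after 12 and after 24 weeks. In a progressive disease the relation could well strengthen with time, and the plan gives no reason for the restriction. If the slopes differ, the Week 24 contrast is adjusted with a blend of the two rather than with its own.

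This matters more than usual for three reasons.

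- **Imbalance is plausible.** There are 11 boys per arm (SAP 2). Minimization uses age and steroid use, not baseline 6MWD (Protocol 3.2.1). Eligibility sets a floor near 75 m and no ceiling (Protocol 4.1).
- **The MMRM is the only planned baseline-adjusted treatment comparison.** SAP 3.4.1 assigns covariate adjustment to it. The t-tests are unadjusted, and the covariance analyses in SAP 6.6 list no treatment term. The MMRM also carries the three dose contrasts, which serve a secondary objective.
- **Point estimates will be read.** Protocol 14.1 says efficacy will be judged on the pattern of the numbers rather than on significance.

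**Working it through.** **Plan's own figure.** There is no powered figure to reproduce. The sample size is 3 x 11 = 33, set by feasibility. No effect size, SD, within-subject correlation or baseline slope is stated.

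**Formula.** Let s12 and s24 be the residual SDs of change, rho their correlation, and b12 and b24 the true baseline slopes. With complete data and a separate mean for each group and visit, the common slope under an unstructured covariance is b_c = w12 x b12 + (1 - w12) x b24, where

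w12 = (s24² - rho x s12 x s24) / (s12² + s24² - 2 x rho x s12 x s24).

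For a between-arm baseline gap D, the Week 24 difference then carries the error

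(b24 - b_c) x D = w12 x (b24 - b12) x D.

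For a dose contrast, replace D by the same contrast of the baseline means.

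**Weight on Week 12** (all inputs assumed):

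| s24/s12 | rho 0.3 | rho 0.5 | rho 0.7 |
|---|---|---|---|
| 0.8 | 0.34 | 0.29 | 0.15 |
| 1.0 | 0.50 | 0.50 | 0.50 |
| 1.2 | 0.63 | 0.68 | 0.79 |
| 1.41 | 0.73 | 0.81 | 0.99 |
| 2.0 | 0.89 | 1.00 | 1.18 |

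Week 12 dominates only when the Week 24 change is the more variable. The fallback structures all assume equal variances, so with two visits they give 50/50.

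**Worked case** (assumed s12 = 35 m, s24 = 48 m, rho = 0.6).

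- s12² = 1225, s24² = 2304 and rho x s12 x s24 = 1008.
- w12 = (2304 - 1008) / (1225 + 2304 - 2016) = 1296 / 1513 = 0.86, so Week 24 gets 14%.

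**Likely gap** (assumed baseline SD 100 m). The SD of a two-arm gap is 100 x sqrt(2/11) = 42.6 m, and the gap exceeds 40 m in about 35% of trials.

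**Error at a 1-SD gap:**

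| b24 - b12 | w12 = 0.86 | w12 = 0.50 |
|---|---|---|
| 0 | 0 m | 0 m |
| 0.05 | 1.8 m | 1.1 m |
| 0.10 | 3.7 m | 2.1 m |
| 0.20 | 7.3 m | 4.3 m |

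**Simulation, 3000 trials of 3 x 11.** With slopes 0.05 and 0.15, the Week 24 estimate shifted by 8.4 m per 100 m of gap under the planned model and by 0.1 m with BASE*AVISITN. With equal slopes, the SD of the Week 24 difference was 20.7 m against 20.8 m.

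**Second simulation** (400 runs per setting, baseline SD 80 m, s12 = 25 m, rho = 0.7). The dependence column is the regression of the Week 24 estimate on the baseline gap.

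| s24/s12; slopes | Dependence, planned | Dependence, with term | SD, planned | SD, with term |
|---|---|---|---|---|
| 1.41; 0 and 0.1 | 0.092 | -0.008 | 15.4 m | 15.1 m |
| 2.0; 0.05 and 0.25 | 0.222 | -0.011 | 22.6 m | 21.4 m |
| 1.41; 0.1 and 0.1 | 0.031 | 0.029 | 14.5 m | 14.8 m |

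With no treatment effect, the mean estimates of both models in the unequal-slope settings stayed close to zero (-1.4 to 0.5 m).

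**The case against.** A common slope is a recognised, simpler specification, and no document shows that the slopes differ. The error is small beside the noise. Added in quadrature to an SD of 20.7 m, shifts of 1.8, 3.7 and 7.3 m inflate it by about 0.4%, 1.5% and 6%. A 100 m gap would be about 2.3 SD and would arise in roughly 2% of two-arm comparisons. SAP 6.1 also repeats the t-tests and the MMRM within baseline 6MWD below and above 350 m, which narrows the baseline range. All of this stands, and it keeps the point modest. It gives no reason to leave out a one-parameter term that removes the dependence on the gap.

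A reader might infer three stronger things that the documents do not support.

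- **That the primary comparison is affected.** The primary analysis is descriptive and the t-tests use no slope.
- **That an unstructured covariance in itself hands the slope to Week 12.** That requires a larger residual variance at Week 24. It is plausible here but not documented.
- **That the treatment effect is biased.** The error follows the realised baseline gap and averages to zero over randomizations.

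The objection about cost also stands in part. The negligible cost was shown only for the two-visit 6MWD model. BIA and lean body mass have seven post-baseline visits. There an unstructured covariance already needs 7 x 8 / 2 = 28 parameters for about 33 boys, and the new term would add six slopes.

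**Conclusion.** The point holds as a cheap improvement to a secondary, exploratory model. Text and code both impose one baseline slope on Week 12 and Week 24. If the slopes differ and the arms differ at baseline by chance, the Week 24 estimate and the dose contrasts carry a conditional error and lose a little precision. Under the assumed SDs, correlation and slope differences, the error is about 2 to 7 m at a typical 43 m gap, about 1 to 4 m if the weights are 50/50, and zero if the slopes are equal. None of these inputs comes from the documents.

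**What to change.** In SAP 8.3, for 6MWD, change the MODEL statement to: model AVAL = BASE ATRTN AVISITN ATRTN*AVISITN BASE*AVISITN / ddfm=KR. Add the term to the covariate lists in SAP 6.1. If it is not added, state why a common slope is assumed.

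- **LSMEANS and ESTIMATE lines:** the term requires no change to them. It does not involve treatment, and it cancels from any within-visit treatment contrast.
- **Other endpoints with two post-baseline visits** (the three timed function tests and muscle strength): add it in SAP 6.2.1(2).
- **Endpoints with more visits,** above all BIA and lean body mass: add it only if the model remains estimable. It costs one parameter per visit beyond the first, and that cost has not been tested.
- **Skeletal muscle CT:** no change. With one post-baseline visit the term is redundant.

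For 6MWD the cost is one parameter. With equal slopes the simulated SD rose from 20.7 to 20.8 m, or from 14.5 to 14.8 m under the other set of assumptions.

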## **6.2** Analysis of Secondary Endpoints

## **6.2.1** EFFICACY ANALYSIS

The following analyses will be performed in the PPS and FAS: Analysis will also be conducted in the group combining the low-dose group and the high-dose group excluding the analysis of MMRM and charts.

(1) 6MWD

Analyses will also be conducted with the following baseline definitions when analyses are conducted using the baseline summary and changes of 6MWD excluding the analysis of MMRM.

- (1) Analysis excluding the subjects for whom the value of (6MWD on Day 1 6MWD at screening)/6MWD at screening is 0.2 or higher or -0.2 or lower
- (2) Analysis using the mean value of 6MWD on Day 1 and 6MWD at screening as the baseline value
- Summary statistics will be calculated at each time point for each treatment group. The data at Week 24 will be analyzed with and without the LOCF imputation.
- Summary statistics for the change from baseline to Week 12 will be calculated, followed by a 2-sample t-test between each treatment group and placebo group.
- With respect to the above 2 analyses, subgroup analysis will be conducted for the following items.

Subgroup analysis:Presence or absence of the history of steroid use, age category ( $\geq$ 5 years and
<7 years, and  $\geq$ 7 years), and baseline 6MWD (<350 m, and  $\geq$ 350 m)

- The time course by each time point will be plotted for each treatment group. Similarly, changes from baseline in the PPS will be plotted.
- For 6MWD at baseline in each group and the group combining all groups in the PPS, the correlation coefficient (Pearson) of the %MVI (%) in both legs of muscle volume measurement (skeletal muscle CT) at each time point will be calculated. See Table 10.1 Method to Derive %MVI (%) for derivation of %MVI (%) of the muscle volume measurement (skeletal muscle CT).
- For the changes in 6MWD from baseline to each time point in each group and the group combining all groups in the PPS, the correlation coefficient (Pearson) of the %MVI (%) in both legs of muscle volume measurement (skeletal muscle CT) will be calculated.
- (2) The following analyses will be performed for each value measured in each motor function test (time to rise from the floor test, Timed 10-m walk/run test, Timed Up & Go test), measurement of muscle volume (skeletal muscle CT, BIA), lean body mass, quantitative muscle strength assessments (hip flexion/extension, knee flexion/extension, ankle extension/flexion), serum CK concentration (only the serum CK concentration during the hospitalization period will be used for the efficacy evaluation), and pulmonary function test (VC, FVC, FEV1.0, FEV1.0%): In the analysis of the muscle volume measurement (skeletal muscle CT) in the PPS, the subjects of the reference values will be excluded. See Table 10.1 Method to Derive %MVI (%) for derivation of %MVI (%) of the muscle volume measurement (skeletal muscle CT). In quantitative muscle strength assessments, the maximum values in the measurement without compensation will be used.
  - Summary statistics will be calculated at each time point for each treatment group.
  - Summary statistics for the change from baseline will be calculated, followed by a 2-sample t-test between each treatment group and placebo group at each time point. The data at Week 24 will be analyzed with and without the LOCF imputation.
  - With respect to the above 2 analyses, subgroup analysis will be conducted for the following items.

Subgroup analysis: Presence or absence of the history of steroid use, age category ( $\geq$ 5 years and <7 years, and  $\geq$ 7 years), and baseline 6MWD (<350 m, and  $\geq$ 350 m)

- The treatment effect will be estimated at each time point using the MMRM. The changes from baseline in the values measured at other time points will also be included in this analysis. Covariates will be the assigned group, baseline value, time point, and the interaction term of the assigned group and time point.
- Using the MMRM, the dose relationship will be analyzed at each time point with treatment contrasts of (placebo group, low-dose group, high-dose group) = (-2 1 1), (-1 0 1), and (-1 -1 2). Covariates will be the assigned group, baseline value, time point, and the interaction term of the assigned group and time point.
- For the above 2 analyses, %MVI (%) of muscular amount measurement (skeletal muscle CT) will be analyzed in the PPS by adding age and the presence or absence of the history of steroid use to explanatory variables. In addition, subgroup analysis will be conducted for the following items. Subgroup analysis: Baseline 6MWD (<350 m, and ≥350 m)

- The time course by each time point will be plotted for each treatment group. Similarly, changes in the muscle volume measurement (skeletal muscle CT) from baseline in the PPS will be plotted.

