# 4. Patient Inclusion/Exclusion and Subject Discontinuation Criteria

#### 4.1 Inclusion Criteria

Patients who meet all of the criteria below at the enrollment will be included in the study. The rationale is described in Section 14.3.

- (1) A legal guardian (legal representative) of a male pediatric patient with the ability to give consent provides written informed consent to participate in the study (whenever possible, informed voluntary assent should also be obtained personally from the patient after all information has been given in a way that suits the patient's level of understanding).
- (2) Patients with a diagnosis of dystrophinopathy as determined by a dystrophin genetic test or muscle pathology findings, symptoms or signs characteristic to DMD (e.g., proximal muscular weakness, waddling gait, Gowers sign), and progressive walking difficulty at the time of informed consent.
- (3) Patients aged 5 years or more at the time of informed consent
- (4) Patients weighing  $\ge$  7.5 kg and < 60 kg within 14 days before enrollment
- (5) Patients who can rise from the floor or a chair and walk by themselves at the screening test (confirmed by medical interview, actual performance, etc.), with 6MWD of 75 m or more (use of wheelchair in daily activities is permissible)
- (6) Patients who can stay in the hospital for the time period specified in the study
- (7) Patients who can continue with administration of the specified number of tablets
- (8) If the patient is receiving oral steroids for DMD treatment, he had begun the treatment more than 6 months before informed consent, and his symptoms remain stable with no change in the prescription-based dosage regimen of steroids within 3 months

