# 5.2 Evaluation/Test Parameters for Individual Visits

# 5.2.1 Screening Period

# 5.2.1.1 Before Enrollment (Day -14 to Day -1)

- Informed consent/assent
- Subject ID code assignment
- Subject characteristics (evaluation items are shown in Table 5-1 Medical Evaluations/Tests)
- Day of diagnosis of DMD determined
- Medical examination
- Pulse rate, blood pressure, body temperature
- Hematology, biochemistry
- Urinalysis
- 12-lead ECG (Heart rate, QTcF interval, findings)
- Cardiac ultrasonography (echocardiography)
- Pulmonary function test [FVC (measured value, predicted value, and % of predicted value) only]
- Motor function evaluation (6MWD only)
- Evaluation of adverse events
- Concomitant medication/therapy

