### 11.3.1 6MWD Test

The distance the subject can walk as fast as possible in 6 minutes will be evaluated.

The test will be performed using a flat, straight. 25-m track wider than a specified width (a quiet indoor hallway, etc.; the distance will be measured accurately with a tape measure, with marks affixed at both ends and cones placed). The subject will go back and forth along the 25-m distance until completion of the test is announced 6 minutes later (passage time of each 25 m will be recorded). The passage time will be read out to the subject while walking, in a specified timing according to the evaluation procedure. The 6-minute walk distance will be recorded in metric units (distance less than 1 meter will be rounded down). For any subject who falls, information on the time of the fall will be recorded. For details of the preparation, implementation procedures, important points, safety considerations, etc., the evaluation procedure will be followed.

For subjects with 6MWD of less than 75 m in the baseline period, before start of administration in this study, investigational product administration will be started as scheduled (Day 1), and the 6MWD tests after administration (at Weeks 12 and 24) will be performed.

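### The 6MWD MMRM uses one pre-dose test although the SAP already defines a two-test mean baseline for the t-tests; adding a two-test MMRM is a cheap improvement whose gain is modest and not guaranteed

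*SAP*

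**What the plan says.** **Two pre-dose tests.** Table 1 of the protocol marks 6MWD at screening and again on Day 1, where baseline assessments are in principle done before the first dose. Screening 6MWD is an entry criterion (Protocol 4.1), so every enrolled boy should have one. Protocol 11.3.1 has a separate rule that opens "For subjects with 6MWD of less than 75 m in the baseline period, before start of administration in this study", which shows that the Day 1 test is distinct from the screening test.

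**Alternative baselines.** Under the t-test bullet, SAP 6.1 adds: "Analyses will also be conducted with the following baseline definitions". The first drops boys whose two values differ by 20% or more. The second reads: "Analysis using the mean value of 6MWD on Day 1 and 6MWD at screening as the baseline value".

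**The MMRM.** The two MMRM bullets in SAP 6.1 do not repeat those definitions. They state: "Covariates will be the assigned group, baseline value, time point, and the interaction term of the assigned group and time point". The SAS code in 8.3 has one such term, footnoted "BASE: Baseline value". The SAP never says outright that the default is Day 1. That follows from the wording of the alternatives and from SAP Table 4.2, which places the baseline window after enrollment.

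**The secondary-endpoint section.** SAP 6.2.1(1) applies the alternative definitions to analyses "using the baseline summary and changes of 6MWD excluding the analysis of MMRM". No reason is given.

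**Role of the MMRM.** The primary analysis is descriptive statistics by group (SAP 5). The MMRM is secondary; it estimates the treatment effect and carries the dose contrasts (-2 1 1), (-1 0 1) and (-1 -1 2).

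**The concern.** The SAP treats a single baseline walk test as fallible: it plans for boys whose two results disagree and offers their average. It then leaves that average out of the one model that adjusts for baseline. The t-tests have no covariates, and the 6MWD ANCOVAs in SAP 6.6 have no treatment term. So the baseline-adjusted treatment estimate and the dose contrasts rest on one test.

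Measurement error in a baseline covariate leaves variance in the outcome that a better baseline would remove. With 11 boys per arm, fixed by feasibility, precision is scarce and the second value is already collected. Both tests precede dosing, so using both does not bias the randomised comparison.

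**Working it through.** **Inputs from the documents.** 33 boys, 11 per arm (SAP 2; 3 × 11 = 33, the only planning figure to reproduce); two pre-dose tests; outcomes at Weeks 12 and 24. No SD, correlation or reliability figure is given, so all magnitudes below rest on assumptions.

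**Assumptions.** True between-boy SD sT = 80–100 m; single-test error SD se = 15–35 m; SD of true 24-week change sp = 30–60 m. Each pre-dose test is the true level plus independent error. Week 24 is the true level plus true change plus error.

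**Step 1: baseline-adjusted residual variance at Week 24.** With the mean of k tests as covariate:

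R(k) = VY − sT⁴/(sT² + se²/k), where VY = sT² + sp² + se².

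Centre case (sT 90, se 25, sp 45): VY = 8100 + 2025 + 625 = 10750.
- Day 1 only: 10750 − 65,610,000/8725 = 3230.2
- Two-test mean: 10750 − 65,610,000/8412.5 = 2950.9

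| sT, se, sp (m) | R(1) | R(2) | Variance ratio | SE ratio |
|---|---|---|---|---|
| 100, 35, 30 | 3216.3 | 2702.1 | 0.840 | 0.917 |
| 90, 25, 45 | 3230.2 | 2950.9 | 0.914 | 0.956 |
| 80, 15, 60 | 4042.4 | 3935.6 | 0.974 | 0.987 |

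The first and last rows are the extremes of the range. Variance falls by about 3% to 16% and SE by about 1% to 8%. In sample-size terms, 33/0.974 = 33.9 and 33/0.840 = 39.3, or about 1 to 6 boys.

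**Step 2: what the planned t-test already gives.** Change from the two-test mean has variance sp² + se² + se²/2 = sp² + 1.5se². At the centre this is 2025 + 937.5 = 2962.5, or 2962.5/3230.2 = 0.917 of the Day 1 MMRM, against 0.914 for the two-test MMRM. The t-test therefore recovers (3230.2 − 2962.5)/(3230.2 − 2950.9) = 96% of the reduction, and 89% to 99% over the whole range. This compares residual variance with complete data only. The t-test has 11 + 11 − 2 = 20 degrees of freedom; a three-arm model with one covariate has 33 − 3 − 1 = 29.

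**Step 3: check in correlation form.** Let ρ be the correlation of each pre-dose test with Week 24, and r the correlation between the two pre-dose tests. The SE ratio of two-test mean to Day 1 is √{[1 − 2ρ²/(1 + r)]/(1 − ρ²)}.

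| ρ, r | SE ratio | Simulated MMRM |
|---|---|---|
| 0.9, 0.9 | 0.88 | 0.88 |
| 0.8, 0.8 | 0.90 | 0.89 |
| 0.8, 0.9 | 0.95 | 0.95 |
| 0.8, 0.95 | 0.98 | 0.98 |

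The simulation used two visits, unstructured covariance, one common baseline slope, 11 per arm, complete data and 1,500 runs. The first two rows show larger gains than Step 1 because, under the Step 1 model, ρ = r means no boy-to-boy variation in true change. In this form the mean-baseline t-test does not always match the Day 1 MMRM: at ρ = 0.8, r = 0.95 its variance factor is 1 + 1.95/2 − 1.6 = 0.375 against 1 − 0.64 = 0.36, an SE ratio of 1.02.

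**Step 4: when the mean does not help.** Steps 1 to 3 treat the two tests as equally predictive, so they cannot show a loss. If Day 1 and screening correlate with Week 24 at ρ1 and ρ2, the mean leaves 1 − (ρ1 + ρ2)²/[2(1 + r)].
- ρ1 = 0.80, ρ2 = 0.75, r = 0.90: 1 − 2.4025/3.8 = 0.368 against 0.36, SE ratio 1.01.
- ρ1 = 0.80, ρ2 = 0.70, r = 0.80: 1 − 2.25/3.6 = 0.375 against 0.36, SE ratio 1.02.
- Break-even at ρ1 = 0.80, r = 0.90: ρ2 = 0.80√3.8 − 0.80 = 0.76.

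The same appears in metres. Give screening extra boy-specific variation of SD d (learning, drift, setting), which adds d²/4 to the variance of the mean. The centre-case variance ratio becomes 0.94 at d = 20 m and 1.02 at d = 40 m.

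**Step 5: screening as a second covariate.** Its weight is estimated, so a weak screening value does less harm. The SE ratios in the first two cases of Step 4 become 0.99 and 0.99 before the lost degree of freedom. When the tests are equally predictive, charging that degree of freedom as 29/28 gives variance ratios from 0.840 × 29/28 = 0.870 to 0.974 × 29/28 = 1.008: a 13% gain to a 1% loss.

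**The case against.** The strongest reply is that the plan already captures most of the gain. SAP 6.1 runs the two-test-mean t-test in PPS and FAS, with and without LOCF, and also for the combined low- and high-dose group. That covers high dose against placebo, the (-1 0 1) contrast, and essentially (-2 1 1). Only (-1 -1 2) has no counterpart. This stands, and Step 2 puts figures on it. What remains is that the t-tests supply neither the MMRM's repeated-measures handling of missing visits nor its variance pooled over three arms.

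Second, screening may not be interchangeable with Day 1. It can fall up to 14 days before enrollment, and Day 1 up to 14 (exceptionally 16) days after. Day 1, Week 12 and Week 24 are hospital tests in a fixed order, whereas screening includes no other motor test. An average learning effect is shared by all arms, but variation between boys in learning is noise. This also stands, and it is why the gain cannot be promised.

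A reader might infer three stronger things that the documents do not support:
- **Precision is lost on the primary analysis.** That analysis is descriptive, and Protocol 14.1 says efficacy is to be judged on numerical trends without needing statistical significance. No decision rule depends on the MMRM standard error.
- **6.2.1(1) is what bars the two-test MMRM.** That section lists no 6MWD MMRM, so its exclusion removes nothing there, and deleting those words alone would change no listed analysis. The restriction comes from where 6.1 places the definitions.
- **The trial forgoes up to six boys' worth of information.** That figure compares MMRM with MMRM and ignores the planned t-tests.

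**Conclusion.** The point holds as a cheap improvement. The 6MWD MMRM uses one baseline test while a two-test baseline, already defined in the SAP and already collected, is confined to the t-tests. Using it would cut the MMRM's Week 24 residual variance by about 3% to 16% (SE by about 1% to 8%) if the assumed SDs are roughly right and screening predicts Week 24 about as well as Day 1 does. If screening is clearly the weaker predictor, the mean baseline gives no gain or a loss of 1% to 2% in SE in the cases tried. The benefit falls on the baseline-adjusted estimate and the dose contrasts, chiefly (-1 -1 2).

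Making the two-test model the headline estimate does not follow automatically: the plan's baseline window lies after enrollment, and the advantage is small. Nor should the argument be carried over to FVC, for which the SAP defines no two-test baseline and no calculation has been made here.

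**What to change.** In SAP 6.1 and 8.3, before unblinding:

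1. State explicitly that the default BASE for 6MWD is the Day 1 value.
2. Add one further 6MWD MMRM, for the treatment effect and all three dose contrasts, in PPS and FAS. Choose one form in advance: (a) BASE = mean of screening and Day 1, with change measured from that mean; or (b) Day 1 kept as BASE, with screening 6MWD as a second covariate. Form (a) spends no degree of freedom but fixes equal weights; form (b) spends one and protects against a less predictive screening test.
3. Report it beside the Day 1 MMRM and state which is read first.
4. Align 6.2.1(1) so that it no longer excludes the MMRM from the alternative baselines. This must accompany the change in 6.1, because alone it alters no listed analysis.

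The cost is one more model run and a few lines of SAP text, with no new data, visit or burden on the boys. The downside is one more result to interpret, for a gain that is modest and not assured.
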